### 3.5 Participant timeline

|   | T x | T -1 | T 0 | T 0-12 | T 12            | F x  | F x                    | T x |
|---|----------------|-----------------|----------------|-------------------|----------------------------|---|-----------------------------------|----------------|
|   | Enrolment      | Run-in          | Baseline       | Pilot             | End of pilot
(+14 days) | Participant interviews
(end of pilot visit or other suitable time) | 3-month follow-up
(+/- 7 days) | Close out      |
| ENROLMENT:   |                |                 |                |                   |                            |   |                                   |                |
| Eligibility screening   | X              |                 |                |                   |                            |   |                                   |                |
| Eligibility confirmation  | X              |                 |                |                   |                            |   |                                   |                |
| Informed consent  | X              |                 |                |                   |                            |   |                                   |                |
| Training on SHAPES app and connected devices  | X              |                 |                |                   |                            |   |                                   |                |
| Run-in (familiarisation with app and devices)   |                | X               |                |                   |                            |   |                                   |                |
| Contact details (name, address, email, telephone number, alternative contact details, HSC number)   | X              |                 |                |                   |                            |   |                                   |                |
| ASSESSMENT:  |                |                 |                |                   |                            |   |                                   |                |
| Baseline Questionnaires ( Barthel Index; EHFS; Gijon Scale; MARS; BMQ; EQ-5D-5L; GSES; OSSS-3; HLM1; participation measure; WHOQOL-BREF ) Medical history data; Demographic data; Technical data; Laboratory results; Unscheduled care; Current prescribed medication   |                |                 | X              |                   |                            |   |                                   |                |
| During pilot ( collected via SHAPES app ) Blood pressure, heart rate, oxygen saturation, weight (daily); Blood glucose (as directed); Heart failure symptom survey (daily); MARS questionnaire (weekly); Unscheduled care updates (as they occur); Prescribed medication updates (weekly); SHAPES app tracking data (continuous); Adverse events; Contact with researchers. |                |                 |                | X                 |                            |   |                                   |                |
| End of pilot Questionnaires ( UEQ-S; SUS; MARS; BMQ; EQ-5D-5L; GSES; OSSS-3; HLM1; participation measure; WHOQOL-BREF; technology acceptance measure ); Demographic data.   |                |                 |                |                   | X                          |   |                                   |                |
| Participant interview  |                |                 |                |                   |                            | X   |                                   |                |
| 3-month follow-up Questionnaires ( EQ-5D-5L; GSES; OSSS-3; HLM1; participation measure; WHOQOL-BREF )   |                |                 |                |                   |                            | X   | X                                 |                |
| HSC Health and social care; EHFS European Heart Failure Self-Care Behaviour Scale; MARS Medication Adherence Report Scale; BMQ Beliefs about Medicines Questionnaire; GSES General Self-Efficacy Scale; OSSS-3 Oslo Social Support Scale-3; HLM1 Single-item Health Literacy Measure; WHOQOL-BREF Abbreviated World Health Organisation Quality of Life questionnaire                     |                |                 |                |                   |                            |   |                                   |                |

Figure 1: Service user participant timeline

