Participants will receive one-on-one, face-to-face introduction to the app and training on how to use both it and the connected medical devices. A user manual will contain detailed step-by-step supportive guidance and information, and will be provided to participants in hard-copy format for reference by participants during the pilot. There will be a run-in period of approximately one week wherein the participant can familiarise themselves with the app and liaise with the researchers to troubleshoot any problems they may be experiencing with the technology. Participants will be asked to use the app and connected devices for 12 weeks. Researchers will contact participants by telephone at the end of week 1, if there are three or more consecutive days where no data has been received (up to a maximum of four times during the pilot) and monthly (if required) thereafter. These telephone contacts are to enable the researchers to support participants with their use of the technology and troubleshoot any issues they may be experiencing (no health advice or clinical support will be provided by the researchers. If participants have any health concerns they will be encouraged to contact their specialist care team).

All data entered or transferred into the SHAPES app (i.e., clinical readings, survey responses) is pseudonymised and will be stored in the technical partners' (EDGE and GNOMON) servers and then uploaded to the SHAPES big data platform. Selected data is then processed by two further SHAPES digital solutions; a heart failure decompensation risk prediction algorithm (VICOM) and an analytic tool that generates personalised dynamic thresholds for participants' clinical parameters (TREE). These digital solutions have not yet been validated or CE-marked for use as medical devices. Therefore, the outputs will not be used to inform clinical care, but rather to determine whether the digital solutions are capable of producing outputs reliably using the available data, and to indicate if there are any associations between the risk scores generated and the participants' use of unscheduled care.

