#### *Secondary outcomes*

- Participants' user experience with the SHAPES app as measured using the User Experience Questionnaire –short version (UEQ-S)
- Usability of the SHAPES app as measured using the System Usability Scale
- Number and rate of successful registrations of each clinical parameter per participant, per day (heart rate, blood pressure, weight, oxygen saturation, blood glucose)
- Number and rate of control limits (upper and lower) successfully generated by the 'Vitals Control' analytic tool per person (rate defined as number of pairs of limits generated per week during the pilot)

- Number and rate of heart failure decompensation prediction (HFPred) risk scores successfully generated per person (rate defined as number of scores generated per week during the pilot)
- Change in hospitalisation rate per person (hospitalisations/month) and A&E attendance rate (attendance/month) three months prior to baseline compared with 3 months during the pilot
- Participants' self-reported medication adherence as measured using the Medication Adherence Report Scale (MARS) at baseline and at the end of the pilot
- Participants' beliefs about medicines as measured using the Beliefs about Medicines Questionnaire (BMQ) at baseline and at the end of the pilot
- Correlation between participants' self-reported medication adherence and beliefs about medicines
- Number and rate (score/week) of heart failure decompensation prediction (HFPred) risk scores successfully generated per person during the pilot
- Correlation between HFPred scores and unscheduled care during the pilot (unscheduled care defined as composite of hospitalisations, A&E attendances, specialist contacts, out-of-hours contacts)
- Health-related quality of life as measured using the EQ-5D-5L questionnaire (ref) at baseline and at the end of the pilot
- Exploration of healthcare practitioners' views on integration and alignment of the SHAPES platform and Digital Solutions with current care pathways
- Exploration of healthcare practitioners' views about their trust and acceptance of the SHAPES platform and Digital Solutions
- Exploration of participants' views about their trust and acceptance of the SHAPES app.
- Exploration of user engagement behaviors

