##### *Service user prior to baseline procedures*

- Screening
- Eligibility confirmation
- Informed consent
- Training on use of SHAPES app and connected devices
- Run-in, familiarisation with devices
- Contact details — name, address, email, phone number, alternative contact name and phone number, Health and Care number

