- Tracking data — log data on how the participant uses the SHAPES app e.g., date/time of usage, what functionalities were accessed
- Adverse events — date, start time, injury description, incident description, action taken, location of incident (private home or healthcare facility)
- Researchers will document any contact received/provided regarding support required to facilitate the pilot (date, duration, reason)

*Service user end of pilot visit (+14 days)*

- Questionnaires — UEQ-S, SUS, MARS, BMQ, EQ-5D-5L, GSES, OSSS-3, HLM1, participation measure, WHOQOL-BREF, technology acceptance measure
- Participant may participate in an interview at this time or a separate date may be accommodated.
- Demographic data — marital status, occupational status, caregiver status, housing details

*Service user follow-up study visits and procedures*

- If an interview is to be conducted this may occur at a mutually convenient time after the intervention has been completed.
- 3 month follow-up data collection (+/- 7days):
- Questionnaires — EQ-5D-5L, GSES, OSSS-3, HLM1, participation measure, WHOQOL-BREF

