#### 4.8 Ancillary and post-trial care

At the end of the pilot the devices provided to participants will be removed and participants will be requested to remove the SHAPES app from their phone/tablet. The exception to this may be the blood glucose meter as the meter used in this pilot is becoming the standard meter distributed in NHSCT. This will be decided on a case by case basis with their diabetes care team.

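### Figure 1 schedules adverse events and unscheduled-care updates only from T0 to T12, yet device use starts about a week earlier, and that week is counted in the three-month before period

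*Protocol*

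**What the plan says.** **Collection schedule.** Figure 1 (protocol 3.5) has one row for data collected during the pilot. It includes "Unscheduled care updates (as they occur") and ends with "SHAPES app tracking data (continuous); Adverse events; Contact with researchers". Its only mark is under T0-12. In 3.8.1, neither item appears in the list of procedures before baseline, at the end-of-pilot visit or at the three-month follow-up.

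**Exposure.** Section 3.3 states: "There will be a run-in period of approximately one week wherein the participant can familiarise themselves with the app". Section 3.8.1 lists "Run-in, familiarisation with devices" among the procedures before baseline. Figure 1 puts training on the app and devices at enrolment, run-in at T-1 and baseline at T0. Section 3.3 then gives the main period: "Participants will be asked to use the app and connected devices for 12 weeks".

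**Comparison.** The secondary outcome for hospitalisation and A&E attendance sets "three months prior to baseline compared with 3 months during the pilot". Table 1 uses the same anchor.

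**Incidents and stopping.** Section 3.8.4 applies the Trust's incident policy to any incident that a participant reports spontaneously, and 4.4 stops the pilot on evidence of harm. Neither sets a time window.

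**Device return.** Section 4.8 says: "At the end of the pilot the devices provided to participants will be removed". Section 3.8.1 heads the closing visit "Service user end of pilot visit (+14 days"), while 4.4 defines the end of the pilot as the last follow-up of the last participant.

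**The concern.** A safety window should cover the time during which participants are exposed, and a before period should not contain time on the intervention. Here the schedule starts at T0 although the devices are in the home and in use before that. Two things follow.

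- **Safety record.** An incident in run-in has a reporting route in 3.8.4 but no place in the collection schedule. The stopping criterion in 4.4 names device malfunction as an example of harm, and 3.2 excludes people with a rubber allergy or a worn or implanted electronic medical device. The protocol therefore foresees device-contact risk, and first contact falls in run-in.
- **Before/after comparison.** Section 3.8.4 tells participants who are concerned by a reading to use their normal routes to care. An attendance prompted by a run-in reading would be counted as pre-intervention use.

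In a single-arm study the before period is the only comparator, so its content should be clean.

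**Working it through.** The protocol gives no figure to reproduce on this point: the sample of 30 is pragmatic and no event rate is stated. The check is window arithmetic.

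**Inputs**
- Run-in: about 1 week, taken as 7 days (3.3).
- Pilot: 12 weeks = 84 days (3.3).
- Before period: 3 months = 365.25 / 4 = 91.3 days (3.4).
- Participants: 30 (3.6).

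**1. Share of the before period spent on the devices**

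f = run-in days / 91.3. At 7 days, f = 7 / 91.3 = 7.7%. Because the run-in length is approximate: 5 days gives 5.5% and 10 days gives 11.0%.

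**2. Share of device use outside the scheduled window**

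Run-in only: 7 / (7 + 84) = 7 / 91 = 7.7%, or 30 × 1 = 30 person-weeks.

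**3. Effect on the rate ratio**

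Assume a constant underlying rate and an effect that starts at first device use. The before rate is then a mixture, and

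observed ratio = RR / [(1 − f) + f × RR], with f = 7 / 91.3.

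| True ratio | Observed ratio | Relative shift |
|---|---|---|
| 0.5 | 0.520 | +4.0% |
| 0.7 | 0.716 | +2.4% |
| 0.9 | 0.907 | +0.8% |
| 1.0 | 1.000 | 0 |
| 1.2 | 1.182 | −1.5% |

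The observed ratio always moves towards 1.

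**4. How many admissions are involved**

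Expected run-in admissions = 30 × monthly rate × 7 / 30.44. At assumed rates of 0.05, 0.1 and 0.2 per person-month this gives 0.3, 0.7 and 1.4 admissions in the whole study.

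**5. Device return**

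Section 4.8 ties removal to the end of the pilot. Figure 1 and 3.8.1 use that term for the T12 visit, which may fall up to 14 days late. Section 4.4 uses it for the last follow-up of the last participant. No day of return can be derived from these three places.

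**The case against.** The strongest reply is that nothing is lost. Sections 3.8.4 and 4.4 have no time limit, researchers are in touch with participants during run-in to troubleshoot, and the baseline look-back captures a run-in admission. In 3.8.1 the bullets for adverse events and unscheduled care carry no start or end date, so the T0-12 limit rests on one mark in Figure 1. Placing baseline after a familiarisation period is also a legitimate choice, and these are secondary outcomes in a 30-person pilot whose primary outcome is app openings.

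Most of this stands, and it limits the point to a mismatch and a misclassification. It does not remove it. The Figure 1 row is labelled as during-pilot collection and marked in the pilot column, so label and mark agree, and 3.8.1 gives run-in no item for either type of event.

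Three stronger readings are tempting, and the document does not support them.

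- *Early and late harm is missed.* Spontaneous reports are accepted at any time.
- *Up to 20% of exposure is uncovered.* This adds 14 late days: (7 + 14) / (7 + 84 + 14) = 21 / 105. The 14 days are a visit window. Nothing says that use continues after week 12, so the figure counts possible possession as exposure. The supported share is 7.7%.
- *The comparison is pushed towards a fall, by two events per run-in admission.* On average there is no push without an effect, and a true reduction is understated. Only a true increase is made to look smaller. If T0-12 stays the during period, reclassifying a run-in admission takes one event out of the before period and adds none to the other side.

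**Conclusion.** The point holds as an inconsistency of windows. Adverse events and unscheduled-care updates are scheduled from T0 to T12, device use begins about a week before T0, and the before period ends at T0. About 7.7% of that period is therefore on-device time (5.5% to 11.0% for a run-in of 5 to 10 days).

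The consequence for the rate comparison is minor: about 4% or less of the rate ratio for true ratios between 0.5 and 1.2, always towards 1, and zero if there is no effect. This rests on a 7-day run-in, a constant event rate and an effect that starts with first use. The number of admissions involved is probably about one or fewer, but only under assumed rates.

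The better reason to act is the record itself. The first week of device use should have a defined place in the safety data, and events in it should not be labelled pre-intervention. The end of exposure is undefined rather than shown to be late, because 3.8.1, 4.4 and 4.8 do not agree on what the end of the pilot is.

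**What to change.** - In Figure 1 and 3.8.1, collect adverse events and unscheduled care from device hand-over to device return, so that the schedule agrees with 3.8.4.
- Reconcile the end-of-pilot visit in 3.8.1, the definition in 4.4 and the removal statement in 4.8, and state when devices are returned.
- End the three-month before period for hospitalisation and A&E at device hand-over.
- Keep T0-12 as the planned during period, and report run-in events on a separate line as on-intervention.

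The cost is protocol wording, additional marks in Figure 1 and a changed window on the CRF. Section 3.8.1 already takes unscheduled-care updates from medical notes, so no visit is added. The downside is that the reported incident count may rise slightly.

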### 3.6 Sample size

The target sample size for this pilot study is 30 NHSCT service user participants and up to 5 HSC staff. These sample sizes were selected pragmatically to be as representative as possible of the target population, large enough to provide valid answers and within the scope of the resources available.

### 3.7 Recruitment

#### Recruitment strategy

Heart failure and diabetes are two of the most common chronic conditions affecting older people in Northern Ireland which is one of the reasons why we have included them in this pilot. People with

these conditions are encouraged to learn more about their conditions and self-management is promoted to help maximise health and wellbeing.

No financial incentives will be provided for participating in this pilot.

*Service user screening procedure*

Potential participants will either be identified from hospital in-patient and clinic lists in Antrim Area Hospital by their direct care team or by a project officer from Mid and East Antrim Agewell Partnership (MEAAP). Alternatively they may contact the research team directly from a recruitment poster or the research team may contact potential participants if consent to contact is obtained.

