## 2.4 Pilot design

This is a non-randomised, single-armed, cross-sectional interventional pilot study with an optional qualitative interview component. The pilot will aim to recruit 30 participants who will be NHSCT service users.

Separate qualitative interviews will be held with up to 5 clinical leads employed by the Northern Health and Social Care service in Northern Ireland.

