### 3.2 Eligibility criteria

#### *Service user inclusion criteria*

At point of consent;

- Northern Health and Social Care Trust service user
- ≥60 years
- Diagnosed with heart failure and/or diabetes mellitus
- If diagnosed with diabetes mellitus (and not heart failure), treatment includes regular monitoring of blood glucose
- Lives at home or in supported living accommodation (category 1 or 2).
  - Category 1 - self-contained accommodation for the more active elderly, which may include an element of scheme supervisor support and/or additional communal facilities
  - Category 2 - scheme supervisor supported self-contained accommodation for the less active elderly, which includes the full range of communal facilities
- Has stable self-reported Wi-Fi connection at home
- Has access to an appropriate android smartphone or tablet
  - Android device running version 6 or above; supports Wi-Fi; supports BLE; front facing camera for facial recognition
- Self-reported stable disease state, the participant feels well enough to take part in the pilot
- Self-reported confident user of smartphone/tablet

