| To validate the capability of the SHAPES platform and Digital Solutions to implement a personalised approach to achieve safe and effective use of medicines in homes.                         | Number and rate of successful registrations of each clinical parameter per participant, per day (heart rate, blood pressure, weight, oxygen saturation, blood glucose)                                      | End of pilot   |
|  | Number and rate of control limits (upper and lower) successfully generated by the 'Vitals Control' analytic tool per person (rate defined as number of pairs of limits generated per week during the pilot) | End of pilot   |
|  | Number and rate of heart failure decompensation prediction (HFPred) risk scores successfully generated per person (rate defined as number of scores generated per week during the pilot)                    | End of pilot   |
|  | Number and rate of views of medication list (rate as defined as number of views per week during the pilot)  | End of pilot   |
| To validate the capability of the SHAPES platform and Digital Solutions to achieve better patient outcomes by initiating, developing and sharing best practice with regards to medicines use. | Change in use of unscheduled care related to heart failure and diabetes as measured by: 
 
• Rate of hospitalisation
 
• Rate of A&E attendance
 
   | 3 months prior to baseline and end of pilot
3 months prior to baseline and end of pilot |

|  |   |                           |
|--|---|---------------------------|
| To validate the capability of the SHAPES platform and Digital Solutions to address and improve deficiencies with adherence to medicines and treatments.                            | Medication Adherence Report Scale (MARS)  | Baseline and end of pilot |
|  | Beliefs about Medicine Questionnaire (BMQ)  | Baseline and end of pilot |
|  | Correlation between participants' self-reported medication adherence and beliefs about medicines  | After pilot               |
| To validate the capability of the SHAPES platform and Digital Solutions to improve data collection to develop predictive algorithms for heart failure decompensation.              | Number and rate of heart failure decompensation prediction (HFPred) risk scores successfully generated with complete data collection per person (rate defined as number of scores generated per week during the pilot)  | End of pilot              |

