**Northern Health and Social Care Trust (NHSCT)**

**Screening** Members of the direct care team will screen their patient lists for potentially eligible participants.

**Invitation** The first communication about the pilot will be from the direct care team at the hospital or via a poster advertising the SHAPES pilot that will be displayed on information boards located within NHSCT Hospitals and on official NHSCT, MEAAP and MOIC social media feeds. The poster will direct potential participants interested in the pilot to contact the research team directly. Alternatively, the direct care team may invite potentially eligible participants to participate in-person at a clinic/hospital attendance, over the phone or via a written invitation (electronic or paper).

**Information sheets** Information sheets will be provided to potentially eligible participants in-person or via post or email either by the direct care team or the research team (if contacted directly or consent to contact is documented). A minimum of 24 hours will be provided to allow time to consider the information provided before consent is obtained.

**Consent to contact** Verbal consent to be contacted may be provided by potential participants to their direct care team to allow the provision of contact name and telephone number of the potential participant to the research team. This will be documented by the direct care team. The research team may then attempt to contact the potential participant by phone.

**Eligibility confirmation** Eligibility may be confirmed by the direct care team. The research team may also confirm eligibility if potential participants make direct contact with them or if participants have provided consent to contact. Eligibility may be confirmed either in-person or over the phone and documented.

**Consent** Eligible participants will be required to provide written consent. The direct care team may obtain consent. The research team may obtain consent if contacted directly by the potential participant or if verbal consent to contact has been received. Voluntary, informed consent for all participants may be obtained in-person or remotely with the following format of signatures collected where appropriate:

- Handwritten
- Typewritten
- Scanned
- An electronic representation of a handwritten signature
- Handwritten signature posted to research personnel

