##### *Service user baseline procedures*

- Questionnaires — Barthel Index, Gijon Scale, EHFS, MARS, BMQ, EQ-5D-5L, GSES, OSSS-3, HLM1, participation measure, WHOQOL-BREF
- Medical history data — height, weight, left ventricular ejection fraction, heart rhythm, implanted devices, medical conditions, heart failure stage, dyspnoea level, smoking status, leg pain symptom question
- Demographic data — including DOB, education, sex, marital status, occupational status, caregiver status, housing details
- Technical data — device monitoring details e.g. model, manufacturer, serial number and preferred time of day for reminders/questionnaires, make and model of the participants own smartphone/tablet
- Laboratory results — urea, creatinine, sodium, potassium, haemoglobin, cholesterol, eGFR, HbA1c, ACR, urine creatinine, urinary albumin-creatinine ratio
- Unscheduled care — hospitalisations (previous 3 months), and previous month hospital readmissions, A&E attendances, out of hours care, specialist service contacts, emergency ambulance call outs

- Current prescribed medication — name, frequency, strength, chronic or as required, stop date if stopped during the pilot, start date if started during the pilot.

*Service user study visits and procedures*

- During the pilot, the participant will be asked to record the following at least once daily, as appropriate, via the SHAPES app; blood pressure, heart rate, oxygen saturation, weight (which will include body mass index, body fat, visceral fat, skeletal muscle, basal metabolic rate).
- Participants diagnosed with diabetes and monitoring blood glucose regularly will be requested to record their blood glucose with the same frequency as directed by their doctor on the SHAPES app.
- Participants diagnosed with heart failure will be asked a series of daily questions about their heart failure symptoms administered via the SHAPES app.
- All participants will be asked about their adherence to medication with a weekly MARS questionnaire administered via the SHAPES app.
- During the pilot, the patient may view their medication list
- Unscheduled care updates — any updates to baseline hospitalisations, hospital readmissions, A&E attendances, out of hours care, specialist service contacts, emergency ambulance call outs recorded from medical notes
- Prescribed medication updates — any updates to prescribed medications notified by participant

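### The admission through which an in-patient is identified can fall in the 'before' window of the single-arm hospitalisation comparison, and each one counted shifts that secondary outcome towards a fall

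*Protocol*

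**What the plan says.** - **Design (2.4).** "This is a non-randomised, single-armed, cross-sectional interventional pilot study". The target is 30 service users (3.6).
- **Recruitment (3.7).** "Potential participants will either be identified from hospital in-patient and clinic lists in Antrim Area Hospital by their direct care team". Clients of a community partnership, poster responders and people who consent to contact are also eligible routes. The split between routes is not given. Within the Trust, "the direct care team may invite potentially eligible participants to participate in-person at a clinic/hospital attendance", and at least 24 hours must pass between information and consent.
- **Eligibility (3.2).** "Self-reported stable disease state, the participant feels well enough to take part in the pilot". No interval since discharge is specified.
- **Timing (3.3, 3.5).** "There will be a run-in period of approximately one week wherein the participant can familiarise themselves with the app". Baseline comes after it.
- **Outcome (3.4, secondary outcomes).** "Change in hospitalisation rate per person (hospitalisations/month) and A&E attendance rate (attendance/month) three months prior to baseline compared with 3 months during the pilot".
- **The same outcome in Table 1 (3.4).** "Change in use of unscheduled care related to heart failure and diabetes", measured by the rates of hospitalisation and A&E attendance.
- **Baseline record (3.8.1).** "hospitalisations (previous 3 months), and previous month hospital readmissions, A&E attendances, out of hours care", followed by further types of contact.
- **Analysis (3.8.11).** Baseline and end-of-pilot values are compared by paired t-test, signed-rank test or a suitable alternative. Intervals and effect sizes are described, for outcomes in general, as estimating a treatment effect.

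**The concern.** A person found on an in-patient list has, by the manner of finding, had an admission shortly before enrolment. If that admission is counted in the 'before' period, selection has supplied an event that the pilot period has no built-in equivalent for. In a controlled trial both arms would share this. Here there is only one arm, so it passes straight into the before/after difference.

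In Table 1, hospitalisation and A&E rates are the only measures mapped to the objective on better patient outcomes, and the same kinds of event are among those mapped to reduced professional workload. If several participants come from in-patient lists, an app without effect could appear to reduce admissions.

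**Working it through.** The protocol gives no hospitalisation rate, effect size or alpha, so there is no planned figure to reproduce.

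**1. Can the index admission fall in the window?** The shortest stated path from information to baseline is 24 hours plus about 7 days, or about 8 days. Taking three months as 91 days, an admission up to 91 − 7 = 84 days before the run-in starts lies inside the look-back. A person identified as an in-patient and enrolled promptly therefore carries that admission into it. The protocol neither excludes it nor moves the window.

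**2. Would it be counted?** Under the secondary-outcome wording, any hospitalisation counts. Under Table 1, it counts only if it was unscheduled and related to heart failure or diabetes, so a planned or unrelated admission drops out.

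**3. Size on the protocol's own scale.** One extra event in three months adds 1/3 per month to that person's 'before' rate. With k such people among 30, the mean change shifts by −k/(3 × 30) = −k/90 per person-month.

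| k (assumed) | Shift, hospitalisations per person-month |
|---|---|
| 1 | −0.011 |
| 3 | −0.033 |
| 5 | −0.056 |
| 10 | −0.111 |

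This needs no assumption about the underlying rate. Simulation under no app effect returns the same shifts.

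**4. Illustration only: relative fall and false positives.** Assume Poisson counts, the same true monthly rate λ for everyone in both periods, and two-sided 0.05. With m = 90λ and N ~ Poisson(m), the expected relative fall is 1 − m·E[1/(k + N)]. Rejection is for an exact signed-rank test.

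| k | Expected fall, λ = 0.02 / 0.05 / 0.10 | Rejection, λ = 0.02 / 0.05 / 0.10 |
|---|---|---|
| 1 | 17% / 1% / 0% | 0.4% / 2% / 3% |
| 3 | 60% / 35% / 20% | 4% / 6% / 5% |
| 5 | 73% / 50% / 33% | 21% / 15% / 11% |
| 10 | 85% / 68% / 51% | 87% / 64% / 43% |

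These figures are fragile. If the k index patients instead have an assumed ongoing rate of 0.30 per month in both periods, rejection at k = 10 drops to roughly 30 to 40%, while the k/90 shift is unchanged. The choice of test matters too: at k = 3 the normal approximation gives 8 to 17%.

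**5. Selection in the other direction.** Suppose the other 30 − k recruits, chosen while feeling stable, have a 'before' rate lower by a share s. With L = 3λ, the net bias in events is k − (30 − k)·L·s, which is zero at k = 30·L·s/(1 + L·s). For an assumed s = 0.5 and λ = 0.02, 0.05 and 0.10, that is k = 0.9, 2.1 and 3.9.

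**The case against.** The strongest reply is that handling of an index event commonly belongs in an analysis plan. The protocol refers to a Data Analysis Plan and a data plan, neither of which is shown. In-patient lists are only one source, and nothing says how many participants, if any, will come from them. Entry also requires people to feel stable and well enough, which may offset the effect. Table 1's restriction removes planned and unrelated admissions. The wording about a treatment effect in 3.8.11 is generic and does not name this outcome.

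Most of this stands as a limit on size and scope. It does not remove the point: the recruitment source, the two windows, the single arm and the general interpretation of before/after differences are all set in the protocol. Followed as written, they push each counted index admission in one direction.

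A reader might infer more: that the trial will report a false fall, or that its false-positive rate is inflated to some stated level. The documents do not support that. They give no k, no rate and no alpha, and they leave the test open. Even on the equal-rate model with the exact test, rejection clearly exceeds 0.05 only from about k = 4 (8 to 11%). Nor does it follow that the A&E rate is biased to the same degree, since a linked attendance need not exist or be counted.

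**Conclusion.** The point holds in a limited form. Index admissions can enter the 'before' count, and each one that is in scope contributes −0.011 hospitalisations per person-month to the mean change with no app effect. That figure rests only on 30 analysed participants and a three-month window. The total depends on k, which is unknown, and the net bias depends also on opposing selection, so it could be trivial or substantial. Relative falls and rejection rates are illustrations under assumed rates, alpha and test.

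A&E attendance may be affected in the same way, with less certainty. The primary outcome, app openings, is not affected. Nor is the economic outcome, which uses costs during the pilot only.

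Two conflicts in the text are separate from this mechanism but govern what is counted. Event scope is unrestricted in the secondary-outcome list and restricted in Table 1. The A&E look-back is three months in both of those places but can be read as one month in the baseline procedures. A one-month record could not support a three-month comparison.

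**What to change.** - Record each participant's recruitment route and the date of any index admission on the CRF, if the data plan does not already hold them.
- Report the change in hospitalisation rate, and in A&E rate where an attendance is linked, both with and without the index event, as a descriptive result.
- State in 3.8.11 that before/after changes in healthcare use are within-person changes and do not estimate a treatment effect. Removing the index event does not replace a control arm.
- Separately, use one event scope in the secondary-outcome list and Table 1, and make the A&E look-back in 3.8.1 agree with the outcome definition.

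The cost of the first three is about one CRF field, one extra set of figures and a change of wording. The sponsor must also accept that the reported reduction may be smaller. Recruitment, eligibility and sample size stay as they are.
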